There are centers in the United States that have developed protocols using erythropoietin to minimize blood product transfusions before and after surgery, also referred to as "bloodless surgery"[4]. There have been retrospective studies evaluating the success of these protocols, but there are no randomized controlled prospective studies that have studied the effects of erythropoietin in patients with cyanotic heart disease in regards to transfusion prevention. There have also been multiple studies looking at the efficacy of EPO in the premature infant population (Donato 2005). In these studies, EPO has been shown to prevent blood transfusions. However, these findings did not represent a clinically significant difference for the study population in the long term. The clinical significance is enhanced in our study population, because blood transfusions may have significant implications for transplant candidacy in the future and transplant complications if needed. Last, there is a study involving infants and children with craniosynostosis showing that EPO is safe and can reduce the number of blood transfusions in a surgical group that has high risk for bleeding (Fearon 2001).

C Study Objectives

C1 Primary Aim

Congenital cyanotic cardiac patients require higher hemoglobin concentrations for optimal oxygen delivery. Prophylactic erythropoietin can prevent and/or decrease the amount of blood transfusions needed prior to surgery. We seek to investigate if erythropoietin makes a clinically significant difference in the number of transfusions given to these patients and the morbidity associated with it during the period in which the subjects will be active in the study (from baseline to 14 weeks post initial injection). The primary aim will be assessed when all subjects have completed week 14 or discontinued early.

C2 Secondary Aim

We will also look to see if administering erythropoietin makes a clinical significance in the following outcomes during the period in which the subjects will be active in the study

(from baseline to 14 weeks post initial injection): weight gain, oxygen saturations, length of initial hospital stay, and hospital readmissions (related to failure to thrive or cyanosis).

C3 Rationale for the Selection of Outcome Measures

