Transfusions are currently the treatment of choice for clinically significant anemia in the cyanotic congenital heart patient. However, this therapy requires hospitalization and an intravenous line which does not come without risk, in addition to the risks associated with transfusions which include transfusion reactions from blood type incompatibility, antibody sensitization, and infections. Thus, the primary outcome will be to see if the number of transfusions can be reduced by administering erythropoietin.

Although the hemoglobin level, in and of itself, should not affect oxygen saturation measured by pulse oximetry, our anecdotal experience suggest that oxygen saturations in patients with cyanotic heart disease frequently improve after a blood transfusion to increase the amount of hemoglobin. Thus, the secondary outcome of oxygen saturation will be looked at for 2 reasons. First, to ensure that the treatment and control arms are similar at baseline to prevent bias for transfusions based on criteria set below. Second, to determine if our anecdotal experience has any validity.

The secondary outcome of weight gain is appropriate in the setting of infants as this variable has been used to monitor the ability to thrive and meet the body's metabolic demands. It is well established in pediatrics that the neonate and infant should gain 15-30 grams per day for optimal growth. Infants who are cyanotic, already have a deficiency in meeting their metabolic demands due to a reduced oxygen carrying capacity. This is further complicated in the instance of anemia. Thus, infants may have an increased ability to optimize weight gain in the setting of normal, stable hemoglobin levels which may be achieved with erythropoietin.

Often, cyanotic congenital heart defect neonates have prolonged initial hospital stays due to the inability to maintain acceptable oxygen saturations, and transition to adequate oral intake for appropriate weight gain. If the hospital stay is found to be shortened after starting erythropoietin, this may be of clinical and financial significance.

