- Age/adjusted age
- Weight
- Oxygen saturation
- Compliance of medication
- Complete blood count
- Transfusions needed
- Hospitalizations
- Adverse events (Severity, expectedness, and relationship)

G Statistical Plan

G1 Sample Size Determination and Power

This will be a randomized controlled single center prospective study of up to 60 patients to account for drop out rate. There will be a minimum 20 treatment patients and 20 control patients enrolled. This sample size is based on a 2 proportion population formula with the assumption that without treatment about 80% of infants need transfusions (based on our experience), and 40% of infants with erythropoietin will need transfusions.

G2 Interim Monitoring and Early Stopping

Unforeseen inaccuracies in design assumptions, in particular having to do with the number of infants who need transfusions without treatment could lead to decreases in the trial's statistical power to detect treatment effects. Accordingly, an analysis will be conducted to estimate the variance of the estimated difference, between the two arms in regards to number of transfusions. This analysis will be conducted within the intention-to-treat framework under which the primary analysis of the primary endpoint will be conducted.

To allow time for corrective action if necessary, this analysis will be performed approximately after 10 patients have been enrolled in both arms. If necessary, this method will be used to obtain a recommended increase in sample size.

An interim analysis of futility will also be performed to determine if the study should continue. This will be done when 10 subjects in each arm have completed the study. The study will be terminated if there is no absolute decrease in number of transfusions per subject.

It is possible that the DSMB may consider it necessary to stop the trial early due to safety concerns. To monitor safety, adverse event rates will be compared between the two trial arms and reported to the DSMB.

In addition, the research team will perform an analysis after the first 5 subjects have completed at least 1 intervention in the EPO arm for safety. These 5 patients will serve as a safety population study.

An interim analysis of safety will be done after 10 patients have enrolled and completed each arm to assess any differences in adverse events between the 2 arms. This will be reviewed by the DSMB who will make the determination as to whether any safety concerns mandate early trial termination.

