G3 Analysis Plan

All primary analyses for efficacy will be performed on an intention-to-treat basis. All subjects will be analyzed according to their group assignment regardless of actual treatment received. In addition, both groups will be compared for safety at the end of the study by comparing adverse events and rates of adverse events. In the safety analysis, subjects will only be included if they actually received treatments in that group. (i.e. if a patient on the EPO arm did not get EPO, they should not be included in the analysis of safety in that arm).

G4 Statistical Methods

All data will only be gathered during the period in which the subjects will be active in the study (from baseline to 14 weeks post initial injection).

For the primary aim, we will compare the number of blood transfusions (one 10 ml/kg aliquot = 1 transfusion) between the two groups with a two-proportion z test. With $n = 20$ subjects per group, this test will have 80% power at the $\alpha = 0.05$ significance level to detect a difference. The primary aim will be assessed when all subjects have completed week 14.

We will compare weight gain and the change in oxygen saturation between baseline measurements and the 6 week follow-up with a two sample t-test. We will also use a linear mixed effects model, with a random intercept included to account for within subject correlation, to determine differences in the longitudinal trends in weight and oxygen saturation between groups. The length of the initial stay will be compared between groups with a two-sample t-test. We will treat the number of re-admissions (in regards to failure to thrive and cyanosis) as a categorical variable, and use Fisher's exact test to determine if there is a difference between EPO and control group readmission counts. We will consider the Mann-Whitney U test as a robust alternative to the two-sample t-test if the assumptions of the t-test are not met by the data.

With a sample size of $n = 20$ subjects per group, the t-tests described above will have 80% power at the $\alpha = 0.05$ level to detect an effect size equal to 0.91 times the common standard deviation. For weight change, assuming that the standard deviation of weights at baseline and the 6 week follow-up equal 1.22 and 1.53 (respectively), and assuming a

moderately high correlation between weight measurements within child of $\rho = 0.70$, this translates to a detectable difference of 1.00 kgs.

G5 Missing Outcome Data

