As this study will have an intention to treat model, missing outcome data will default to reflect that the subject has received a transfusion. In addition, there may be additional analysis only reflecting subjects who have completed the study in its entirety.

H Data Handling and Record Keeping

H1 Confidentiality and Security

All data will be kept secure through the UCSD REDCap database provided by the Clinical and Translational Research Institute. REDCap is a customizable secure Web based database. It can only be accessed with a username and password that is assigned specifically to each research member. Information entered into the data entry system will be by subject study I.D. number. Data will be checked by an automated validation tool on REDCap to ensure proper data entry. A project has been created in that database for this particular study.

H2 Training

Before the study is started, each member must complete certification requirements to conduct research and show demonstration of familiarity with study procedures, methods for endpoint measurement, use of the database management system to conduct the study.

H3 Case Report Forms and Source Documents

The case report forms (both inpatient and outpatient) will be used as the source documents. The case report form that will be used can be found in section L3.

H4 Records Retention

All data will be kept secure through the UCSD RED Cap database. Hard copies of the case report forms will be stored in binders that will be kept in secure areas in the research office.

I Study Monitoring, Auditing, and Inspecting

I1 Study Monitoring Plan, Auditing and Inspecting

Interim monitoring will be performed as outlined in section G2. In addition, throughout the entire study, data will be collected and compiled on a weekly basis. Data will be entered into the database at least monthly. The research team will review to ensure that the data is being obtained properly, entered into the database properly and to look for any missing data at least quarterly. A safety report will be submitted to the DSMB for review at least quarterly.

J Study Administration

J1 Organization and Participating Centers

University of California, San Diego
Rady Children's Hospital, Heart Institute

J2 Funding Source and Conflicts of Interest

This study is currently funded by the Academic Enrichment Grant from the Rady Children's Hospital foundation.

J3 Committees

Research team:

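### The primary variable is not uniquely defined: the aims, G4 and the futility rule count transfusions, but the test and sample size need one yes/no result per infant

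*Combined protocol and SAP*

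**What the plan says.** All references are to the combined protocol and SAP.

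Pointing to a count:
- C1 asks whether erythropoietin "makes a clinically significant difference in the number of transfusions given to these patients". C3 says "the primary outcome will be to see if the number of transfusions can be reduced by administering erythropoietin". The E1 design summary uses the same variable.
- G4, defining the main comparison: "we will compare the number of blood transfusions (one 10 ml/kg aliquot = 1 transfusion) between the two groups with a two-proportion z test". The transfusion guidelines (E2, item 2.i) also work in 10 ml/kg aliquots, so an infant transfused twice counts twice.
- G2, variance look: "an analysis will be conducted to estimate the variance of the estimated difference, between the two arms in regards to number of transfusions". G2, futility rule, applied when 10 subjects per arm have completed: "The study will be terminated if there is no absolute decrease in number of transfusions per subject".

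Pointing to a yes/no result per infant:
- G1 uses a two-proportion formula and assumes that "without treatment about 80% of infants need transfusions (based on our experience), and 40% of infants with erythropoietin will need transfusions", with at least 20 infants per arm.
- G4 names a two-proportion z test and claims 80% power at alpha 0.05 with 20 per group.
- G5 sets the rule that "missing outcome data will default to reflect that the subject has received a transfusion". This is most naturally yes/no, although it could mean a count of one.
- G2 explains its variance look by possible errors in the design assumptions, "in particular having to do with the number of infants who need transfusions without treatment". That is a number of infants, but the variance it then estimates is for a number of transfusions.

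A2 and C1 speak of both preventing transfusions and reducing their amount, which covers either reading.

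**The concern.** The primary outcome, its test, its sample size and its stopping rule should all refer to the same quantity. Here they do not, and the mismatch sits inside the one G4 sentence that defines the primary analysis.

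Two things are at stake. First, the trial is open-label (E2 item 2.d; E3 item 3.h), and J3 gives the principal investigator responsibility for data collection and analysis. With two defensible primary variables, the choice could be made after the results are visible. Second, G2 words the futility rule as a termination, and it acts on the count, for which the plan offers no design assumption.

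**Working it through.** **Inputs.** From G1: 80% and 40% of infants transfused, 20 per arm. From G4: alpha 0.05, power 80%. From E2 item 2.d: 1:1 allocation. Sidedness is not stated; I take two-sided.

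**Step 1: reproduce the plan's figure on the yes/no endpoint.** With unpooled variance,

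n per arm = (z₀.₉₇₅ + z₀.₈₀)² × [p₁(1−p₁) + p₂(1−p₂)] / (p₁−p₂)²
= (1.960 + 0.842)² × (0.16 + 0.24) / 0.16
= 7.85 × 2.5 = 19.6, rounded up to 20.

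Power at 20 per arm = Φ(0.40 / √(0.40/20) − 1.960) = Φ(2.828 − 1.960) = Φ(0.868) = 80.7%. Exact enumeration gives 81.5%. The stated 20 per arm and 80% power therefore rest on the proportion of infants transfused.

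**Step 2: try the same for the count.** Any such calculation needs the mean number of aliquots per infant in each arm and its variance or dispersion. The documents give neither, so no n or power can be derived. Assumed distributions show how open this is, at 20 per arm and with 80% versus 40% of infants having at least one aliquot:
- Poisson counts have means −ln(0.2) = 1.61 and −ln(0.6) = 0.51. Power is about 89% for a rate comparison and about 91% for a rank-sum test.
- If transfused infants in both arms receive 1 + Poisson(0.5 to 2) aliquots, rank-sum power is 64% to 66%.

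The result falls on either side of 80% depending on an assumption the plan does not make. These figures are illustrations only.

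**Step 3: can the two variables disagree at the futility look?** Take 10 completers per arm:

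| | Infants transfused | Aliquots each | Total aliquots | Aliquots per subject |
|---|---|---|---|---|
| Control | 8 of 10 | 1 | 8 | 0.8 |
| EPO | 4 of 10 | 2 | 8 | 0.8 |

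On yes/no this is 80% versus 40%, exactly the design effect. On G2's count per subject there is no decrease, and the rule terminates the trial.

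**Step 4: how often would futility stop wrongly?** With 80% versus 40% true, 10 per arm, and a stop if EPO is not below control, the probability is 4.4% on yes/no (exact). On counts it is about 7% to 8% under the assumed 1 + Poisson(0.5 to 2) aliquots.

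**Step 5: the disagreement also runs the other way.** Suppose 80% are transfused in both arms, with 1 + Poisson(2) aliquots in one and 1 + Poisson(0.5) in the other. The means are 0.8 × 3 = 2.4 and 0.8 × 1.5 = 1.2 per infant. At 20 per arm the two-proportion test then has 5% power and a rank test on counts about 66% (assumed distributions, simulated). The two variables answer different questions.

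**The case against.** The strongest reply is that any competent analyst will read G4 as at least one transfusion. Nearly everything numerical fits: the two-proportion formula, the 80% and 40% of infants, the named test, its power, the natural sense of G5, and the prevention half of A2 and C1. This stands as far as it goes. A reader might infer that the primary outcome has no valid test at all. The documents do not support that, because a workable yes/no reading exists and its sample size checks.

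Three things remain. The aliquot definition has no purpose in a yes/no test. Where G4 does convert a count, it says so: readmissions are explicitly treated as categorical, and nothing similar is said for transfusions. And the inferred reading leaves G2 unrepaired, because futility would still be judged per subject on the count.

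A second reply is that the futility harm is modest, and that a futility stop with no efficacy claim does not raise the type I error. Both are correct.

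A third point limits the evidence. The case report form section that would show how transfusions are recorded is not visible to me, so I can say only that no visible passage settles the question.

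A reader might also apply the z test literally to aliquots over infants. The control proportion then passes 1 once the 16 expected transfused controls (0.80 × 20) average more than 20/16 = 1.25 aliquots. This shows that the literal wording cannot be carried out. It does not show that a wrong result would be reported, since the failure would be obvious.

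**Conclusion.** The concern holds as a problem of definition: two primary variables are in use and neither is stated to govern. The stated sample size and power are sound for the yes/no endpoint (19.6 per arm, 80.7%), given 80% versus 40%, a two-sided test and unpooled variance.

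A reader might infer that the trial is underpowered for the count. The documents do not support this. Power there is unknown, and assumed distributions put it above or below 80%.

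The practical size is an open choice of primary endpoint in an unblinded trial, and a terminating rule on a variable the trial was not sized for. The chance of a wrong futility stop is 4.4% on yes/no against about 7% to 8% on counts, the latter under assumed distributions. Whether the z test uses pooled or unpooled variance is a separate point and carries no weight here.

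**What to change.** Make these changes before any between-arm look at transfusion data:

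- Define the primary outcome as whether the infant received at least one transfusion from baseline to week 14 (yes/no).
- Keep the two-proportion test and 20 per arm.
- Reword C1, C3, E1, G4 and G5 to match.
- Base G2's sample-size re-estimation and futility rule on that proportion.
- Make aliquots per infant a secondary count outcome, analysed by rank-sum or negative binomial.

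The cost is wording only. The yes/no result can be derived from the transfusion item already listed in F6. The secondary count needs aliquots on the case report form, which I could not check. The small downside is that the primary test ignores repeat transfusions.

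Keeping the count as primary is possible but is not the cheap route. It needs a count test, a new sample-size justification from a stated mean and dispersion, and a count-scale rule for missing data in G5. The 80% versus 40% assumption would no longer support the sample size.

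### At 20 per arm, the primary test's stated 80% power and a two-sided 5% level do not hold together, and G4 does not say which z test is meant

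*Combined protocol and SAP*

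**What the plan says.** G1 sets a minimum of 20 infants per arm, with up to 60 enrolled to allow for drop-out. Of the calculation it says: "This sample size is based on a 2 proportion population formula". The assumed rates are that "without treatment about 80% of infants need transfusions" and that "40% of infants with erythropoietin will need transfusions".

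G4 compares the number of transfusions "between the two groups with a two-proportion z test" and states that with 20 subjects per group "this test will have 80% power at the" 0.05 significance level. Neither section says whether the variance is pooled or unpooled, whether a continuity correction applies, or whether the test is one- or two-sided.

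For the secondary t-tests, G4 claims 80% power at the same n and alpha "level to detect an effect size equal to 0.91 times the common standard deviation". G5 counts a missing outcome as a transfusion.

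**The concern.** A z test for two proportions relies on a normal approximation. With 20 per arm, its true false-positive rate can differ noticeably from the nominal 5%, and the size and direction of the difference depend on the variance form. If the form that yields the planned n is also the form that rejects too often, the power claim is bought with a looser alpha than the one stated.

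This is the primary comparison in an unblinded trial. If the form is left open, a borderline result could be significant under one defensible reading of G4 and not under another, and the choice could be made after the data are seen.

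**Working it through.** **Inputs.** Rates of 0.80 (control) and 0.40 (EPO), from G1. n = 20 per arm, alpha 0.05 and power 80%, from G4. Sidedness is not stated for this test.

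**Inferring sidedness.** For the t-test claim (20 per group, 0.91 SD), the non-centrality is 0.91 × √10 = 2.88 on 38 degrees of freedom. Power is 80.1% two-sided and 88.1% one-sided. Only two-sided matches the claimed 80%, so two-sided is used below.

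**Reproducing the plan's figure.**
- Unpooled: n = (0.80×0.20 + 0.40×0.60) × (1.960 + 0.842)² / 0.40² = 0.40 × 7.849 / 0.16 = 19.6, so 20. Power at 20 = Φ(0.40/√(0.40/20) − 1.960) = Φ(0.868) = 80.7%. This matches G4.
- Pooled (mean rate 0.60, 2×0.60×0.40 = 0.48): n = (1.960×√0.48 + 0.842×√0.40)² / 0.16 = 22.3, so 23. Power at 20 = Φ((0.40×√20 − 1.960×√0.48)/√0.40) = 75.2%.
- The arcsine formula gives 22 and the continuity-corrected formula 28.

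Of the two-sided formulas tried, only the unpooled one gives 20.

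**Exact behaviour at 20 per arm.** Each of the 21 × 21 possible outcome pairs is weighted by its binomial probability, and the weights are summed over the pairs where the test rejects. Size uses one common rate in both arms; power uses 0.80 v 0.40.

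| Test (two-sided, nominal 0.05) | True size | Power |
|---|---|---|
| Unpooled z | 6.5-8.1% (common rate 40-80%) | 81.5% |
| Pooled z | 4.3-5.3% (common rate 40-80%) | 75.3% |
| Boschloo | at most 4.6% (any rate) | 72.8% |
| Fisher | at most 2.5% (any rate) | 65.0% |

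For the unpooled test, the size is 7.6% at a common rate of 40% or 60%, 8.1% at 50%, 6.9% at 70% and 6.5% at 80%. The worst case is 8.1/5 = 1.6 times the nominal level.

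**What the choice can do.** Take 14/20 v 8/20 transfused, a difference of 0.30.
- Unpooled: SE = √((0.70×0.30 + 0.40×0.60)/20) = 0.150, z = 2.00, p = 0.046.
- Pooled: SE = √(0.55×0.45×2/20) = 0.157, z = 1.91, p = 0.057.
- Fisher: p = 0.11.

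**Larger n.** With complete outcomes, Boschloo's power is 80.9% at 23 per arm, 83% at 25 and 90% at 30. Counting missing outcomes as transfused moves each rate p to p(1 − m) + m, where m is the missing fraction. The plan gives no m; the values here are assumptions, equal in both arms. At 30 per arm:
- m = 10%: 0.82 v 0.46, power 83%.
- m = 20%: 0.84 v 0.52, power 74%.
- m = one third: 0.87 v 0.60, power 60%.

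**The case against.** A reader might infer that the trial's primary test has a 6.5-8% false-positive rate. The documents do not support that. They never say that the analysis uses the unpooled statistic; matching n = 20 shows only how the sample size was probably derived. If the analysis pools the variance, the level at 20 per arm is essentially nominal and the fault is about 5 points of missing power. Even for the unpooled form, the excess fades at high common rates (5.7% at 85%, 4.0% at 90%).

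A reader might also call 80% a miscalculation. It is not: a standard formula gives it.

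Nor is it shown that no reading can satisfy G4. A one-sided 0.05 pooled z test has 83.8% exact power, with size about 4.2-5.2% at common rates of 40-80%. That objection stands as far as it goes, but G4 does not say one-sided, and its own t-test claim fits only two-sided.

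The futility look in G2 could be offered as protection. If it were binding and applied to proportions (G2 words it as transfusions per subject), overall type I error with the unpooled test would fall to about 3.2-3.9%. Nearly all of that is on the benefit side, where a two-sided 5% test allows 2.5%. The plan does not rely on the look for this purpose.

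Finally, G4 describes the outcome as a number of transfusions, while its test and G1's rates concern proportions. If a count were analysed, none of these figures would apply. That is a reason to define the endpoint, not a defence of the power statement.

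**Conclusion.** The point holds in conditional form. Read as two-sided, G4's 80% power and 0.05 level are not delivered together at 20 per arm by any of the versions tried. The unpooled z test reaches the power at a true size of 6.5-8.1% for common rates of 40-80%. Tests at or near 5% give about 75% (pooled z), 73% (Boschloo) or 65% (Fisher).

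This rests on the inferred two-sidedness, a binary endpoint, G1's rates of 80% and 40%, a fixed-sample analysis and no missing outcomes. The cause is an approximation used at small n together with an unspecified test. The excess for the pooled test is small at 20 per arm, where its main defect is lost power.

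**What to change.** In G4:

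1. Define the primary endpoint for this test as the proportion of infants transfused at least once up to week 14.
2. State that the test is two-sided at 0.05.
3. Name one test that holds its level, for example Boschloo's exact unconditional test. An explicitly pooled z test is a near-nominal alternative at 20 per arm (size at most 5.3%). It is not near-nominal at every n: at 25 per arm its size reaches 6.5% when the common rate is 50%.
4. Restate the power at 20 per arm as about 73% (Boschloo) or about 75% (pooled z), and align G1 with it.
5. If power at larger n is quoted (Boschloo about 81% at 23, 83% at 25 and 90% at 30 per arm), say that it assumes no missing outcomes. G1 holds the extra infants for drop-out, and the G5 rule lowers these figures.

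The cost is SAP wording and a less favourable stated power. No extra data are needed, and 23 per arm (46 infants) is within the planned maximum of 60 if the sponsor wants 80% with complete outcomes.
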